9.4.4.5 Use of the investigational product in case of bleeding/spotting episode

Scheduled bleeding is expected to begin within a few days of taking the last active tablet (i.e. pink tablet), but may begin sooner or later. If spotting occurs while on the usual regimen of one tablet daily, the subject should continue medication without interruption. She should be instructed that this type of bleeding is often transient and without significance. However, if the bleeding is persistent or prolonged, nonfunctional causes may be considered and the subject should be advised to call the Investigator who will decide the best management for the subject. The bleeding profile will be recorded by the subject on a subject diary.

9.4.4.6 Use of the investigational product in the event of a missed menstrual period

A missed menstrual period may occur even if the subject adhered to the prescribed dosage regimen. However, as the contraceptive method used in this study is still under investigation, a rapid detection of any pregnancy is necessary. For this reason, if the subject presents a missed period, she will be instructed to use the home urine pregnancy test provided by the study staff to rule out pregnancy before continuing the contraceptive regimen (see Section 9.6.2).

9.4.5 Blinding

This is an open-label study.

9.4.6 Restrictions

9.4.6.1 Prior and Concomitant Therapy

Medications with an end date occurring before the first investigational product dose date in the treatment period will be identified as prior medications. Medications with a start date occurring on or after the first investigational product dose date in the treatment period or medications

with a start date prior to the first investigational product dose date and an end date on or after the first investigational product dose date will be identified as concomitant medications.

Unauthorized Prior Therapies:

- Use of an injectable hormonal method of contraception within 10 months (300 days) prior to screening for an injection with a 3-month duration, within 6 months (180 days) prior to screening for an injection with a 2-month duration, within 3 months (90 days) prior to screening for an injection with a 1-month duration.
- Use of drugs potentially triggering interactions with COC within one month prior to subjects' enrollment. This includes, but is not limited to:
 - CYP 3A4 inducers: barbiturates, primidone, bosentan, felbamate, griseofulvin, oxcarbazepine, topiramate, carbamazepine, phenytoin, rifampicin, St John's wort.
 - CYP 3A4 inhibitors: azole antifungals, phenylbutazone, modafinil, cimetidine, verapamil, macrolides, diltiazem and grapefruit juice.
 - HIV/HCV protease inhibitors and non-nucleoside reverse transcriptase inhibitors.

Unauthorized Concomitant Therapies:

- Use of any contraceptive method other than the investigational product. Note: use of condoms is only allowed during the course of the study to avoid transmission of sexually transmitted infections (STIs), or in case of missed tablets, or when unauthorized concomitant therapies are used. Condom use must be recorded in the subject diary.
- Daily, long-term treatment for chronic conditions or diseases with medications that may increase serum potassium concentration (e.g. ACE inhibitors, angiotensin-II receptor antagonists, potassium-sparing diuretics, potassium supplementation, heparin, aldosterone antagonist and non-steroidal anti-inflammatory drugs).
- Use of drugs potentially triggering interactions with COC. This includes, but is not limited to:
 - CYP 3A4 inducers: barbiturates, primidone, bosentan, felbamate, griseofulvin, oxcarbazepine, topiramate, carbamazepine, phenytoin, rifampicin, St John's wort.
 - CYP 3A4 inhibitors: azole antifungals, phenylbutazone, modafinil, cimetidine, verapamil, macrolides, diltiazem and grapefruit juice.
 - HIV/HCV protease inhibitors and non-nucleoside reverse transcriptase inhibitors.

These drugs or herbal products may decrease the effectiveness of hormonal contraceptives or increase breakthrough bleeding. Subjects must be instructed to use a back-up contraceptive method when these drugs are used, up to and

including the next 7 days after finishing the concomitant therapy and to record this back-up contraception in the subject diary (see Section 9.6.1). It is the responsibility of the Investigator to ensure that any change in concomitant medications during the study is recorded in the source documentation and entered in the electronic case report form (eCRF).

Warning: oral contraceptives may interfere with the metabolism of other drugs. Accordingly, plasma and tissue concentrations may be affected (e.g. cyclosporine). Consult the prescribing information of concomitant drugs for possible interactions with oral contraceptives.

9.4.6.2 Condoms and other contraceptive methods

Use of condoms is allowed during the course of the study only to avoid transmission of STIs or in case of missed tablet(s) or unauthorized concomitant therapies. Condom use must be recorded in the subject diary. Use of any other contraceptive methods must also be recorded in the subject diary (see Section 9.6.1). The cycles during which condom(s) or other contraceptive method(s) than the investigational product were used will be excluded from the Pearl Index calculation.

9.4.7 Treatment beyond the clinical trial

Post-treatment contraceptive counseling should be given to each subject at Visit 6 and at the Early Termination Visit in case of premature study termination. Post-treatment contraceptive treatment should be started no later than on the day following the last tablet intake of the trial medication.

9.5 Study Activities

The following sections provide details of the study activities which are summarized in the Schedule of Events (Appendix 1). The study will include 1 Screening Visit (Visit 1), 1 enrollment Visit (Visit 2), 4 in-treatment Visits (Visits 3 to 6) and 1 exit Visit (Visit 7).

At any time during the study, an Unscheduled Visit may occur in case of suspicion of pregnancy.

9.5.1 Visit 1: Screening Visit

The subject must be fasting for at least 8 hours (overnight fast) before the Screening Visit. Prior to conducting any screening procedures, subjects will be given a full description of the nature of the study. The purpose, timing, procedures, and risks of the study will be explained to the subject, including requirements for enrollment and participation in the study, medication restrictions during the study, and requirements for washout of certain medications that the subject may already be taking. The eligible subject who is willing to participate in the study will then be required to provide written consent. The Investigator or a designated medically

Amendment Final Version 1.1

qualified member of the study staff will interview potential participants to establish their eligibility for inclusion in the study.

[figure not shown]
Potential subjects will be screened according to the inclusion and exclusion criteria within 45 days prior to the subject enrollment visit (Visit 2). Subjects who were eligible for the study but did not enroll within 45 days of screening (Visit 1) can be re-screened. Re-screening requires all Visit 1 assessments to be repeated. The Investigator will maintain a log of all subjects screened for participation and record the reason(s) for excluding potential subjects.

The following will be performed to determine eligibility:

- 1. Obtain signed IC from subjects. Subjects will receive a copy of the IC (see Section 10.3);
- 2. Review and document inclusion and exclusion criteria (see Sections 9.3.1 and 9.3.2);
- 3. Record demographic information (see Section 9.6.4.4);
- 4. Obtain medical and surgical history (see Section 9.6.4.6);
- 5. Obtain gynecological history including identification of the previous contraceptive method used, if any (see Section 9.6.4.7);
- 6. Obtain prior medication use information (see Section 9.6.4.5);
- 7. Perform a physical examination (see Section 9.6.3.4);
- 8. Perform a gynecological examination including breast examination (see Section 9.6.3.6);
- 9. Obtain cervical cytology (see Section 9.6.3.6);
- 10. Perform a Chlamydia test (see Section 9.6.3.6);
- 11. Perform a gonorrhea test (see Section 9.6.3.6);
- 12. Collect fasting (8-hour) blood samples for hematology, biochemistry and pregnancy test (see Sections 9.6.2.1 and 9.6.3.3);
- 13. Measure vital signs (see Section 9.6.3.7);
- 14. Measure height and weight, and calculate BMI (see Section 9.6.3.5);
- 15. Schedule the next study visit.

FSTMTRA

The Visit 2 will occur within 45 days after the Screening Visit (Visit 1), when the entire laboratory results of the subject have been received.

On the basis of the laboratory results, the Investigator must assess the eligibility of the subject.

In case of positive Chlamydia or gonorrhea test result (see Section 9.6.3.6), the subject will be treated before enrollment. Choice of treatment is left at the Investigator's discretion.

During Visit 2, the following procedures will be performed:

- 1. Review, confirm and document inclusion and exclusion criteria (see Sections 9.3.1 and 9.3.2);
- 2. Obtain prior medication use information (see Section 9.6.4.5 and Section 9.4.6 for restrictions);
- 3. If all screening assessments are acceptable and all inclusion criteria and no exclusion criteria have been met, the subject will be enrolled in the study;
- 4. Perform a Chlamydia and gonorrhea test, if indicated (see Section 9.6.3.6);
- 5. Measure vital signs (see Section 9.6.3.7);
- 6. Dispense investigational products for Cycle 1-4 and one spare blister pack and give the subject the instructions for use (see Section 9.4.4.2);
- 7. Dispense subject diary and give the subject the instructions for use (see Section 9.6.1);
- 8. Dispense home urine pregnancy test kits with the instructions for use. Subject should perform a urinary pregnancy test just before the intake of the first pink tablet, preferably with first urine in the morning. The result has to be recorded in the diary. The subject should only start with the trial medication when the pregnancy test is negative (not pregnant). If the pregnancy test is positive, the subject should not take any trial medication and contact the Investigator. The Investigator should arrange for an Unscheduled Visit (see Section 9.5.5) to confirm the pregnancy, complete the Pregnancy Report Form if the pregnancy is confirmed (see Section 9.6.2.1) and the subject should be withdrawn;
- 9. Query the subject as to the occurrence of any AE(s) and record any AE(s) observed or spontaneously volunteered by the subject (see Section 9.6.3.1);
- 10. Dispense the questionnaires and give the subject the instructions for completion (see Section 9.6.4.11);

- 11. Schedule or confirm the next study visit and the follow-up phone call;
- 12. Instruct the subject to come to the next visit with her subject diary and the unused investigational product, including empty blisters, spare and boxes;
- 13. Instruct any subject not on a hormonal contraceptive and who does not start the investigational product at the enrollment visit to contact the site immediately if her next menses occurs at earlier than 21 days or is delayed such that her cycle length exceeds 35 days, and that she should not start the investigational product if either of these happens;
- 14. Instruct the subject to contact the site immediately if she decides to discontinue the investigational product and, if possible, to not discontinue the investigational product before contacting the site;
- 15. Complete a follow-up call within 7 days following the expected start date of the treatment to remind the subject to complete the diary entries.
- 9.5.3 Treatment Period (from Cycle 1 Day 1 until Cycle 13 Day 28)
 - 9.5.3.1 Visit 3 (Cycle 2, between Day 1 and Day 14)

- 1. Perform a Chlamydia and gonorrhea test, if indicated (see Section 9.6.3.6);
- 2. Measure vital signs (see Section 9.6.3.7);
- 3. Query the stop date of the previous contraceptive method;
- 4. Investigational product return and drug accountability (see Section 9.4.1.2);
- 5. Collect and review completed subject diary pages and return the diary to the subject (see Section 9.6.1);
- 6. Ensure appropriate completion of the questionnaires;
- 7. Collect blood samples from the subjects participating in the Population PK Substudy according to the sampling scheme outlined in Section 9.6.4.2. *Note that Visit 3 for the subjects in the Population PK Substudy should be performed between Days 10 and 14*;
- 8. Query the subject as to the occurrence of any TEAE(s) and record any TEAE(s) observed or spontaneously volunteered by the subject (see Section 9.6.3.1);
- 9. Obtain concomitant medication use (see Section 9.6.4.5 and Section 9.4.6 for restrictions);

- 10. Schedule or confirm the next study visit;
- 11. Instruct the subject to come to the next visit with her subject diary and the unused investigational product, including empty blisters, spare and boxes;
- 12. Instruct the subject to contact the site immediately if she decides to discontinue the investigational product and, if possible, to not discontinue the investigational product before contacting the site.

9.5.3.2 Visit 4 (Cycle 4, between Day 1 and 14)

- 1. Perform a Chlamydia and gonorrhea test, if indicated (see Section 9.6.3.6);
- 2. Measure vital signs (see Section 9.6.3.7);
- 3. Measure weight and calculate BMI (see Section 9.6.3.5);
- 4. Collect blood samples from the subjects participating in the Population PK Substudy according to the sampling scheme outlined in Section 9.6.4.2. *Note that Visit 4 for the subjects in the Population PK Substudy should be performed between Days 10 and 14*;
- 5. Investigational product return and drug accountability (see Section 9.4.1.2);
- 6. Dispense investigational products for the next 3 cycles and remind the subject the instructions for use (see Section 9.4.4.2);
- 7. Collect and review completed subject diary pages and return the diary to the subject (see Section 9.6.1);
- 8. Query the subject as to the occurrence of any TEAE(s) and record any TEAE(s) observed or spontaneously volunteered by the subject (see Section 9.6.3.1);
- 9. Obtain concomitant medication use (see Section 9.6.4.5 and Section 9.4.6 for restrictions);
- 10. Schedule or confirm the next study visit;
- 11. Instruct the subject to come to the next visit in a **fasted state**, with her subject diary and the unused investigational products, including empty blisters, spare and boxes;
- 12. Instruct the subject to contact the site immediately if she decides to discontinue the investigational product and, if possible, to not discontinue the investigational product before contacting the site.

9.5.3.3 Visit 5 (Cycle 7, between Day 1 and 14)

The following procedures will be performed:

- 1. Perform a Chlamydia and gonorrhea test, if indicated (see Section 9.6.3.6);
- 2. Measure vital signs (see Section 9.6.3.7);
- 3. Measure weight and calculate BMI (see Section 9.6.3.5);
- 4. Investigational product return and drug accountability (see Section 9.4.1.2);
- 5. Dispense investigational products for the next 3 cycles and remind the subject the instructions for use (see Section 9.4.4.2);
- 6. Collect and review completed subject diary pages and return the diary to the subject (see Section 9.6.1);
- 7. Query the subject as to the occurrence of any TEAE(s) and record any TEAE(s) observed or spontaneously volunteered by the subject (see Section 9.6.3.1);
- 8. Obtain concomitant medication use (see Section 9.6.4.5 and Section 9.4.6 for restrictions);
- 9. Collect fasting (8-hour) blood samples for biochemistry (see Sections 9.6.3.3);
- 10. Schedule or confirm the next study visit;
- 11. Instruct the subject to come to the next visit with her subject diary and the unused investigational products, including empty blisters, spare and boxes;
- 12. Instruct the subject to contact the site immediately if she decides to discontinue the investigational product and, if possible, to not discontinue the investigational product before contacting the site.
 - 9.5.3.4 Visit 6 (Cycle 10, between Day 1 and 14)

- 1. Perform a Chlamydia and gonorrhea test, if indicated (see Section 9.6.3.6);
- 2. Measure vital signs (see Section 9.6.3.7);
- 3. Investigational product return and drug accountability (see Section 9.4.1.2);
- 4. Dispense investigational products for the next 3 cycles and remind the subject the instructions for use (see Section 9.4.4.2);

- 5. Collect and review completed subject diary pages and return the diary to the subject (see Section 9.6.1);
- 6. Dispense the questionnaires and give the subject the instructions for completion (see Section 9.6.4.11);
- 7. Query the subject as to the occurrence of any TEAE(s) and record any TEAE(s) observed or spontaneously volunteered by the subject (see Section 9.6.3.1);
- 8. Obtain concomitant medication use (see Section 9.6.4.5 and Section 9.4.6 for restrictions);
- 9. Give the subject counseling about the next contraceptive method to use at the end of the study (see Section 9.6.4.9);
- 10. On the day the subject is expected to start the next contraceptive method $(\pm 1 \text{ day})$, perform a follow-up call to ensure subject's compliance with this method (see Section 9.6.4.9).
- 11. Schedule or confirm the next study visit;
- 12. Instruct the subject to come to the next visit in a **fasted state** with her subject diary and the unused investigational products, including empty blisters, spare and boxes;
- 13. Instruct the subject to contact the site immediately if she decides to discontinue the investigational product and, if possible, to not discontinue the investigational product before contacting the site.
- 9.5.3.5 Visit 7 (Cycle 14, between Day 16 and 23), End of Treatment Visit

- 1. Perform a physical examination (see Section 9.6.3.4);
- 2. Measure weight and calculate BMI (see Section 9.6.3.5);
- 3. Perform a gynecological examination including breast examination (see Section 9.6.3.6);
- 4. Collect fasting (8-hour) blood samples for hematology, biochemistry and pregnancy test (see Sections 9.6.2.1 and 9.6.3.3);
- 5. Measure vital signs (see Section 9.6.3.7);
- 6. Investigational product return and drug accountability (see Section 9.4.1.2);

Amendment Final Version 1.1

- 7. Collect and review completed subject diary pages (see Section 9.6.1);
- 8. Ensure appropriate completion of the questionnaires;
- 9. Query the subject as to the occurrence of any TEAE(s) and record any TEAE(s) observed or spontaneously volunteered by the subject (see Section 9.6.3.1);
- 10. Obtain concomitant medication use (see Section 9.6.4.5 and Section 9.4.6 for restrictions);
- 11. Complete the End of Study Form.

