- 37. History of alcohol or drug abuse (including laxatives) within 12 months prior to screening.
- 38. Any prior procedure, disease or condition that could result in altered absorption, excessive accumulation, impaired metabolism, or altered excretion of the investigational product.
- 39. Uncontrolled thyroid disorders.
- 40. Participation in another investigational drug clinical study within 1 month (30 days) or have received an investigational drug within the last 3 months (90 days) prior to study entry. Subjects who participated in an oral contraceptive clinical study, using FDA/EU approved active ingredients, may be enrolled 2 months (60 days) after completing the preceding study.
- 41. Sponsor, the Contract Research Organization (CRO) or Investigator's site personnel directly affiliated with this study.
- 42. Is judged by the Investigator to be unsuitable for any reason.

Investigational Product; Dose; and Mode of Administration:

The investigational product is a 15 mg E4/3 mg DRSP tablet administered orally once daily in a 24/4-day regimen (i.e. 24 days of active tablets followed by 4 days of placebo tablets).

Duration of the study:

Overall treatment duration is up to thirteen 28-day cycles, i.e., 12 months.

Those subjects who discontinue due to a pregnancy wish will be followed-up for a maximum of one year after study discontinuation for return of spontaneous menstruation and until pregnancy or initiation of a contraceptive method (whichever occurs first).

Statistical Methods:

For the efficacy analyses, the pregnancy rates will be expressed as:

- Pearl Index (number of pregnancies per 100 woman years due to method and user failure) with a two-sided 95% confidence interval (CI);
- Method failure Pearl Index (number of pregnancies per 100 woman years due to method failure only) with a two-sided 95% CI;
- Life-table analysis (cumulative pregnancy rate).

For Pearl index calculations, thirteen 28-day cycles constitute one woman-year.

Primary Efficacy Analysis:

Pearl Index for subjects aged 16 to 35 years, inclusive, at the time of screening.

Secondary Efficacy Analyses:

- Method failure Pearl Index and life-table analysis for subjects aged 16 to 35 years, inclusive, at the time of screening.
- Pearl Index, method failure Pearl Index and life-table analysis for the overall study population (16 to 50 years).

Additional Summaries:

- Occurrence of scheduled and unscheduled vaginal bleeding/spotting in the overall study population.

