9.4.4.2 Dosing Instructions

Each time investigational product is dispensed to the subject, site personnel will instruct the subject as follows:

- Take one pink tablet every day for 24 consecutive days (Day 1 through Day 24), followed by one white placebo tablet every day for 4 consecutive days (Day 25 through Day 28).
- When the pack of tablets is empty, start the next pack on the next day after the last white tablet of the previous pack has been taken. When starting a new pack of tablets, take the first pink tablet of the pack. There should be no interruption between two blister packs.
- Take the investigational product at approximately the same time each day throughout the study. The time of day should be determined by the subject.
- Return all blister packs to site personnel at the following visit.

9.4.4.3 Instructions in case of missed tablet(s) or in conditions potentially reducing the contraceptive efficacy

If the subject has vomiting or diarrhea within 4 hours of tablet intake, she should take another tablet from the extra pack (spare blister) as a replacement.

If the subject inadvertently misses one or more of the tablets, the following instructions must be followed⁶:

- If one active pink tablet is late (< 24 hours since a tablet should have been taken) or if one active pink tablet has been missed (24 to < 48 hours since a tablet should have been taken):
 - Take the late or missed active pink tablet as soon as possible.
 - Continue taking the remaining active pink tablets at the usual time (even if it means taking two active pink tablets on the same day).
 - Use of condom is not required.
- If two or more consecutive active pink tablets have been missed (\geq 48 hours since a tablet should have been taken):
 - If between Day 1 & Day 17:
 - Take the most recent missed active pink tablet as soon as possible (any other missed tablets should be discarded).
 - Continue taking the remaining active pink tablets at the usual time (even if it means taking two tablets on the same day).
 - Use condom or avoid sexual intercourse until 7 days of uninterrupted active pink tablet intake.
 - Consider emergency contraception as per current practice if the woman had unprotected intercourse during the missed pill interval.
 - If between Day 18 & Day 24:
 - Omit the hormone-free interval by finishing the active pink tablets in the current pack and starting a new pack the next day.

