9.6.3.3 Clinical Laboratory Evaluations

Methods for blood sample collection, processing, and shipment are described in instructional materials provided to investigational sites.

Any remaining retainable biological samples will be stored at the central laboratory or designee at the latest until the marketing authorization. These samples may be used for future additional analysis in the context of the E4/DRSP development program.

At Visit 1 and 7, blood hematology, biochemistry and lipids will be assessed (see Appendix 2). At Visit 5, the following biochemistry parameters will be assessed: glycaemia, glycated hemoglobin, total cholesterol, HDL- and LDL-cholesterol, triglycerides, Lactate dehydrogenase (LDH) 1 and LDH 2, renal function (urea, creatinine, and glomerular filtration rate [GFR]) and ionogram (Na, K, Cl, Ca²⁺, P, HCO³⁻). Subject should be fasting for 8 hours before blood collection.

All out-of-range laboratory values that are considered by the Investigator to be clinically significant will be recorded as AEs (see Section 9.6.3.1)

Amendment Final Version 1.1

FSTMTRA

A physical examination will be performed at Screening Visit and Visit 7. The physical examination will include an evaluation of the following: body as a whole, skin, head, eyes, ears, nose, and throat (HEENT), neck, cardiovascular, respiratory, musculoskeletal, neurologic, lymphatic/thyroid, abdomen.

When reporting the results of the physical examination, the use of the "Abnormal" category will be reserved for findings that are considered clinically significant, in the opinion of the Investigator; the "Normal" category will include "Abnormal" results that are not clinically significant, as well as no findings.

All abnormal findings will be recorded as AEs (see Section 9.6.3.1).

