12.5.3 Clinical Laboratory Evaluations

For continuous clinical laboratory analytes, the absolute value and change from baseline will be summarized by analyte and visit using descriptive statistics for the Safety population. Categorical laboratory analytes, classified as normal or abnormal, will be summarized by analyte and visit using the number and percentage of subjects in each category for the Safety population. The denominators for calculating the percentages will be based on the number of subjects with non-missing assessments at a particular visit for the Safety population.

Shifts to values outside of the normal range will be presented by analyte and visit and will be summarized by the number and percentage of subjects with evaluable shifts. An evaluable shift is one where both the Screening Visit value and the on-treatment or early termination value are recorded for subjects in the Safety population. The denominators for calculating the percentages will be the number of subjects with an evaluable shift.

All clinical laboratory values, abnormal clinical laboratory values, and clinical significant laboratory values will also be provided in data listings.

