9.6.3 Laboratory Data

Central laboratory data will be used for the tables and listings. The scheduled laboratory assessments will be included in the tables where data are available. If a specific parameter is missing at the scheduled assessment and there is an unscheduled assessment collected at the same visit where this parameter is not missing, then the value at the unscheduled assessment will be used in the table. Otherwise unscheduled assessments will not be included in the tables. Note that unscheduled pregnancy tests will be used in the assessment of pregnancies for the primary endpoint. The parameters listed in **Table 4** will be summarized. Separate outputs will be provided for hematology, serum chemistry and lipid profile.

Table 4: Laboratory Parameters

Hematology	
Hemoglobin	Mean cell volume
Hematocrit	White blood cell & Differential
Red blood cell count	Platelet count
Serum Chemistry	
Albumin	Total protein
Alanine aminotransferase (ALAT)	Serum creatinine
Aspartate aminotransferase (ASAT)	Sodium
Blood urea nitrogen	Potassium
Gamma glutamyl transferase (GGT)	Calcium
Glucose	Chloride
Glycated hemoglobin	Bicarbonate
Lactate dehydrogenase (LDH) 1 and LDH 2	Phosphorus
Total bilirubin	Choriogonadotropin Beta (Serum Pregnancy Test)
Estimated Glomerular Filtration Rate (eGFR)	
Lipid Profile	
Total cholesterol	Triglycerides
High density lipoprotein cholesterol	Low density lipoprotein cholesterol

For continuous clinical laboratory analytes, the absolute value and change from baseline will be summarized by analyte and visit using descriptive statistics for the Safety Population.

Shifts to values outside of the normal range will be presented by analyte and visit and will be summarized by the number and percentage of subjects with evaluable shifts. The denominators for calculating the percentages will be the number of subjects in the Safety Population with both the Baseline value and the value at the specified visit recorded.

If the value is below the lower limit of quantification, then half the lower limit of quantification will be used in the summary tables to calculate the descriptive statistics. If the value is above the upper limit of quantification, then the upper limit of quantification will be used in the summary tables to calculate the descriptive statistics. In the listings, values will be listed as collected without the imputation applied.

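### All haematology and the main liver tests lack a scheduled on-treatment value: the end-of-treatment panel falls 16–23 days after the last tablet, and the Cycle 7 draw omits 12 of 28 laboratory lines

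*Protocol*

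**What the plan says.** **Treatment.** The Protocol synopsis states: "Overall treatment duration is up to thirteen 28-day cycles, i.e., 12 months". The heading of Protocol 9.5.3 sets the period: "Treatment Period (from Cycle 1 Day 1 until Cycle 13 Day 28". Within each cycle, Protocol 9.4.4.2 says: "Take one pink tablet every day for 24 consecutive days (Day 1 through Day 24". Placebo tablets fill the last four days.

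**Laboratory draws.** Protocol 9.6.3.3 places the full panel at two visits: "At Visit 1 and 7, blood hematology, biochemistry and lipids will be assessed (see Appendix 2". The second of these is "Visit 7 (Cycle 14, between Day 16 and 23), End of Treatment Visit". An Early Termination Visit repeats the Visit 7 procedures 16 to 23 days after the last intake (Protocol 9.5.4). The one draw in between is at Visit 5 (Cycle 7, Days 1–14). Its list, in Protocol 9.6.3.3 and footnote 10 of the Schedule of Events, covers glucose, glycated haemoglobin, lipids, LDH 1 and 2, renal function and electrolytes.

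**Next contraceptive.** Protocol 9.4.7 says: "Post-treatment contraceptive treatment should be started no later than on the day following the last tablet intake of the trial medication".

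**Analysis.** Protocol 12.5.3 counts a shift as evaluable when "both the Screening Visit value and the on-treatment or early termination value are recorded for subjects in the Safety population". SAP 9.6.3 says: "Shifts to values outside of the normal range will be presented by analyte and visit". Its denominator is women with a baseline value and a value at the visit in question. Unscheduled results enter the tables only to fill a parameter missing at the same scheduled visit.

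**The concern.** General safety is a stated objective, and routine laboratory parameters are among its named data sources (Protocol synopsis and 8.3). Protocol 7.2 reports very limited to no hepatic impact in Phase 2 and looks to larger populations for further evaluation. This trial of about 2000 women is such a population. For blood counts and the main liver tests, however, it compares a value from before treatment with one taken after the drug has been stopped, when many women will have begun another method.

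The comparison can mislead in two ways. A reversible change during treatment may have shrunk before it is measured, so an unremarkable table says little about the treatment period. Conversely, a change caused by the next method may be read as an effect of E4/DRSP.

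**Working it through.** **1. Timing for completers.** Cycles last 28 days, and Cycle 14 Day 1 is taken as the day after Cycle 13 Day 28. Dispensing of 4 + 3 + 3 + 3 = 13 blisters, plus spares (Protocol 9.4.1), confirms that no Cycle 14 treatment is planned.

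- Last active tablet: 12 × 28 + 24 = day 360.
- Last tablet: 13 × 28 = day 364.
- Visit 7: 364 + 16 = day 380 to 364 + 23 = day 387.
- Since last tablet: 380 − 364 = 16 to 387 − 364 = 23 days.
- Since last active tablet: 380 − 360 = 20 to 387 − 360 = 27 days.
- Since the next method was due at the latest (day 365): 15 to 22 days.

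**2. Timing for early leavers.** The draw is due 16–23 days after the last tablet of any kind. With 0 to 4 placebo tablets taken last, that is 16–27 days after the last active tablet. A woman who attends a scheduled visit after 16 or more days off product is sampled then, and no upper limit is given.

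**3. Analyte count.** Urea at Visit 5 is taken to be blood urea nitrogen in Appendix 2.

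| Appendix 2 group | Lines | Drawn at Visit 5 | Not drawn on treatment |
|---|---|---|---|
| Haematology | 6 | 0 | 6 |
| Chemistry | 18 | 12 | 6 (albumin, total protein, ALAT, ASAT, GGT, total bilirubin) |
| Lipids | 4 | 4 | 0 |
| Total | 28 | 16 | 12 (12/28 = 43%) |

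Counting LDH 1 and LDH 2 as two lines gives 12 of 29.

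**4. Women with no on-treatment laboratory value at all.** Protocol 12.1 plans for about 45% dropout among 1800 women aged 16 to 35, with an average of 4 cycles in those who discontinue. A discontinuer who reaches Cycle 7 has contributed at least 6 cycles. If a share p of discontinuers does so, 6p ≤ 4, so p ≤ 2/3. On these planning figures, at least 45% × 1/3 = 15% (270 women) and at most 45% (810 women) leave before Cycle 7.

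**5. How much of an effect could remain.** The documents give no reversal rates, so a range of half-times h is assumed. The share left after t days is 2^(−t/h).

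| Assumed half-time | t = 16 (earliest early-termination draw) | t = 20 | t = 27 |
|---|---|---|---|
| 2 days | 0.4% | 0.1% | below 0.1% |
| 7 days | 21% | 14% | 7% |
| 14 days | 45% | 37% | 26% |

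**6. The shift definition.** Visit 7 lies outside the SAP 5.3 on-treatment periods for efficacy (to 7 days after the last dose) and for medications (to the last dose). Only the adverse-event period, which has no end, covers it. Read strictly, Protocol 12.5.3 gives completers no evaluable shift for the 12 lines, because their Visit 7 value is neither on treatment nor from early termination. Read loosely, it counts an off-treatment value as on treatment.

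**The case against.** The late visit has a plausible purpose. On-treatment conceptions count up to 7 days after the last tablet, and a serum pregnancy test at 16–23 days falls 9–16 days after that window closes. The protocol does not give this reason, but it is a fair one for keeping the visit where it is. It does not explain why blood counts and liver tests are drawn only there.

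Several stronger readings are tempting, and the documents do not support them.

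- **That the SAP presents Visit 7 laboratory data as on-treatment.** It does not. That wording is in Protocol 12.5.3 only. SAP 9.6.3 reports by visit and is silent on the point.
- **That every woman is on another hormonal method by Visit 7.** Women stopping for a pregnancy wish are excepted, and the next method may be non-hormonal. The share on a hormonal method is not given.
- **That any effect would have vanished.** At a 14-day half-time, 26–37% remains at Visit 7, and slow red-cell measures are probably affected less.
- **That on-treatment laboratory safety is unmeasured.** Sixteen lines, including potassium, renal function and lipids, are drawn at Visit 5. Vital signs and weight also have on-treatment values.
- **That the plan intends to claim no effect on liver or blood count.** It promises descriptive summaries only.

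Adverse events are also sought at every visit from Visit 2, and extra tests are allowed at unscheduled visits. These catch overt problems, but not silent changes, and SAP 9.6.3 largely keeps unscheduled results out of the tables.

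**Conclusion.** The concern holds as a design limitation that should be corrected or, failing that, disclosed. For 12 of 28 Appendix 2 lines there is no scheduled on-treatment value. On the plan's own dropout figures, roughly 15–45% of the 16-to-35 group would have no on-treatment value for any line. The post-baseline panel comes 20–27 days after the last active tablet in completers with full Cycle 13 intake, and is due 16–27 days after it in early leavers.

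The timing and the count follow directly from the documents, given the stated reading of Cycle 14 Day 1 and of urea. The size of any lost signal does not: it rests on assumed half-times, and the supportable wording is that a reversible change could have partly or largely resolved. Attribution of a next-method effect to E4/DRSP is likewise possible but unquantified.

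**What to change.** **1. Complete the Visit 5 panel.** Add haematology and the six missing chemistry analytes to the fasting draw already taken at Visit 5. This costs one more tube, a few assays and a protocol amendment, which under Protocol 13.2 needs competent-authority and IRB approval, across up to about 80 centres. If Visit 5 has passed, run the six chemistry analytes on retained Visit 5 samples where these exist, since Protocol 9.6.3.3 allows later analysis within the development programme. The laboratory would need to confirm sample stability. Haematology could not be recovered.

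**2. Label the off-treatment results.** Reword the shift definition in Protocol 12.5.3. In the SAP 9.6.3 tables, mark Visit 7 and Early Termination laboratory results as post-treatment, and show them by whether a hormonal method had been started. SAP 5.6 and 9.3.3 already classify and list post-study contraceptives. Keep these results in the tables. Base on-treatment laboratory statements on Visit 5, and say that Visit 5 covers only women still on treatment at Cycle 7.

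**3. Weight and examinations.** Keep the Visit 4 and Visit 5 weights as on-treatment values, and label Visit 7 weight and examinations post-treatment. A rule restricting everything to Visit 5 would not work, because examinations are not done there and weight is also taken at Visit 4.

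The SAP parts of items 2 and 3 need only SAP text and table labels; the Protocol 12.5.3 wording can go into the same amendment as item 1. If only the labelling is done, nothing can be said from scheduled data about on-treatment values of the 12 lines, and the report should state this.
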